Objectives:	
Principal aim: SAFETY
 
The primary objective of the study is to confirm the safety of a marketed auricular spray with reverse and microdiffusion nozzle by clinical examination by ENT specialist and by the scoring of the irritation of the ear canal at D60 in comparison with basal scoring of irritation at D0 (scale 0 to 3) such as:
 
 
- 0: no irritation,
 
- 1: slight irritation (located slight erythema and/or dryness),
 
- 2: moderate irritation (clear erythema or dryness which may be visible on the whole treated area),
 
- 3: severe irritation (serious erythema with potential oedema and/or scar).
 
 
Potential adverse events collection.
 
Secondary aims: EFFICACY/PERFORMANCE PREVENTION for investigational device with reverse nozzle, investigational device with microdiffusion nozzle and for control group, in comparison to the baseline (D0) and between groups:
 
 
• scoring of the obstruction of ear canal by the Investigator
 
 
0: no obstruction – normal and/or no significant presence of cerumen in the ear canal. The membrane is clearly visible.
 
1: <25% minimal, very little and mostly insignificant impacted cerumen. The tympanic membrane is visible, but with still a little bit cerumen.
 
2: 25-50% mild, some excessive impacted cerumen causing partial occlusion of the ear canal. The tympanic membrane is not entirely visible, quite difficult to see.
 
3: 50-75% moderate, moderate and excessive impacted cerumen causing partial occlusion of the ear canal. Partial to very little of the tympanic membrane is visible.
 
4: 75-100% severe, severe and excessive impacted cerumen causing partial or complete occlusion of the ear canal. Little if any of the tympanic membrane is visible.
 
 
• audiogram with classification of the loss or gain hearing function using the following scale (only for subjects more than 6):
 

YSLAB	Medical Device CIP #23E1670	Final version 2.0 Date: 09/11/2023	Confidential Page 11/64
-------	--------------------------------	---------------------------------------	----------------------------

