	
No hearing function loss, hearing function loss between 5 to 10dB, hearing function >10dB (Subha et al.2006), hearing function win between 5 to 10 dB, hearing function win >10dB.
 
Additionally, the secondary objective of this study will be to see if the investigational device is more efficient in children, adults or elderly subjects (for both nozzles - reverse or microdiffusion).
 
 
• Subject's self-evaluation using a questionnaire.
 
• Evaluation of the effect on the number of auricular affection (such as otitis) during the use period (daily log).
 

Design:	Open study, randomized, before / after treatment, with tested product versus control group, in parallel groups
Planned Sample Size:	
99 included subjects and results delivered on 90 subjects.
 
 
• 1 group of 72 included subjects in order to have results on 66 subjects (33 subjects using product with the "reverse diffuser" and 33 using the product with the "microdiffusion diffuser")
 
• 1 group of 27 included subjects in order to have results on 24 subjects not using a spray (control group). (in case of discomfort or pain, they are allowed to use ear drops prescribed by a doctor after a medical examination)
 

Number of investigational study sites:	2 centers
Inclusion criteria:	
 
1. Gender: female and/or male.
 
2. Age: 
 
- 30 to 40% having age between 3 to 12 yo,
 
- 30 to 40% between 13 to 65 yo,
 
- 30 to 40% more than 65 yo.
 
 
 
3. Subjects able to use the tested product.
 
4. Subjects having history of cerumen occlusion more than once a year with or without symptoms (reduction of hearing function, obstruction feeling of the ear canal,..).
 
5. Subjects having ear help system or regular users of systems such as anti-noise plugs or headsets (only for the 13yo subjects and more).
 
6. Subjects having a clinical score of ear canal obstruction of 2 or 3 at D0.
 

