Statistical methods:	
The analysis of the primary endpoint will be performed on the ITT and population.
 
The analysis of the secondary endpoint will be performed on the population.
 
The analysis of the safety/tolerance parameters will be performed on "safety" population.
 
Primary endpoint:
 
The irritation is assessed by the Laryngologist using a 4-point structured scale (from "No irritation (0)" to "Severe irritation (3)" on D0 and D90).
 
For each product, a paired t-test will be used to test whether the change from baseline (D90-D0) differ significantly from 0. The normality assumption will be checked using a Shapiro-Wilk test (<math>\alpha=0.01</math>), in case of rejection, a Wilcoxon signed ranks test will be used.
 
To test whether the products differ statistically in terms of change from baseline (D90-D0), a two-sided t-test is used. If the normality assumption is not met, a non-parametric approach is used with a Wilcoxon signed rank test.
 
Secondary endpoints:
 
For each secondary parameter:
 
 
• Clinical score of the irritation with structured scale
 
• Clinical score of the obstruction of ear canal
 
• Results of audiogram with classification of the loss or win hearing function.
 
• The number of auricular affection (such as otitis) during the use period
 
 
For each product, a paired t-test will be used to test whether the change from baseline (D90-D0) differ significantly from 0. The normality assumption will be checked using a Shapiro-Wilk test

YSLAB	Medical Device CIP #23E1670	Final version 2.0 Date: 09/11/2023	Confidential Page 13/64
-------	--------------------------------	---------------------------------------	----------------------------

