	
(<math>\alpha=0.01</math>), in case of rejection, a Wilcoxon signed ranks test will be used.
 
To test whether the products differ statistically in terms of change from baseline (D90-D0), a two-sided t-test is used. If the normality assumption is not met, a non-parametric approach is used with a Wilcoxon signed rank test.
 
For the subjective evaluation questionnaire:
 
For each item of the subjective questionnaire, the raw data will be summarized in frequency (N) and percentage (%) by group of product.
 
All statistical tests will be assessed at <math>\alpha = 5\%</math> level of significance in a bilateral approach.
 
Statistical software: SAS® v9.4.

Foreseen study duration:	
Clinical investigation beginning: Q4 2023
 
Clinical investigation end: Q3 2024
 
Clinical investigation global duration: 8 months
 
Duration by subject: 90 days

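### The primary objective concerns one spray with two nozzles, but the synopsis states no irritation analysis of all 66 spray users

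*Combined protocol and SAP*

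**What the plan says.** All references are to section 1.5, the overall synopsis.

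- **Objectives.** The principal aim is to "confirm the safety of a marketed auricular spray with reverse and microdiffusion nozzle", judged by clinical examination, the 0 to 3 irritation score and adverse events. The secondary performance aims name the two nozzle versions and the control group separately.
- **Design.** The tested product, in the singular, is compared with a control group.
- **Planned Sample Size.** The total is "99 included subjects and results delivered on 90 subjects". Spray users are "1 group of 72 included subjects in order to have results on 66 subjects", and the same bullet divides the 66 into 33 per nozzle. The control is "1 group of 27 included subjects in order to have results on 24 subjects not using a spray".
- **Investigational device.** Two entries are listed, one per nozzle.
- **Statistical methods, primary endpoint.** There are two tests of irritation. The first reads "For each product, a paired t-test will be used to test whether the change from baseline (D90-D0) differ significantly from 0", with a signed-rank test if Shapiro-Wilk rejects normality at 0.01. The second compares products on change from baseline. Tests use the 5% "level of significance in a bilateral approach". Safety and tolerance parameters are analysed on the safety population, with no split by nozzle stated.

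**The concern.** The objective asks about the spray, but on the natural reading of *product* the irritation tests answer for each nozzle and for the difference between nozzles. An effect of the spray itself, equal with both nozzles, is absent from the nozzle difference by construction. It can then be seen only in two within-nozzle tests, each with half of the users.

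This matters more for a safety objective than for an efficacy one. A non-significant change is the favourable result here, so lost sensitivity works in the device's favour. If no pooled analysis is prespecified, the choice between split and pooled results could also be made after the data are seen.

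**Working it through.** **Head-count.** 33 + 33 = 66 evaluable spray users; 66 + 24 = 90 evaluable; 72 + 27 = 99 included. The plan's figures agree with each other. The supplied text gives no power, effect size, SD or margin, so the sample size cannot be re-derived from a power calculation. All effect sizes and worsening rates below are assumptions.

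**Which test would run.** The score is an integer from 0 to 3, so changes are small integers with many zeros. For n=33 with 1 to 16 users worsening by one grade and the rest unchanged, Shapiro-Wilk gives p below 0.0000001 in every case, far under 0.01. In data of this kind the plan moves to the signed-rank test.

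**Signed-rank, exact form.** If x users worsen by one grade and none improve, zeros drop out, the ranks are equal, and two-sided p = 2 × 0.5^x.

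- x=5: p = 0.0625
- x=6: p = 0.031
- x=10: p = 0.002

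So 5 of 33 on each nozzle is non-significant twice, and the same users pooled, 10 of 66, are clearly significant. At least 6 worsened users are needed. With worsening rate w, power is P(X ≥ 6) for X binomial(n, w), and the chance that both nozzles miss is (1 − power)².

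| Assumed w | Power, n=33 | Both nozzles miss | Power, n=66 | Pooled miss |
|---|---|---|---|---|
| 10% | 11% | 80% | 66% | 34% |
| 15% | 37% | 39% | 94% | 6% |
| 20% | 67% | 11% | 99.5% | 0.5% |

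**Sensitivity to the form of the test.** The plan does not say whether the signed-rank p-value is exact. In the large-sample form without continuity correction, x equal changes give z = √x. Then x=4 gives p=0.046 and x=5 gives p=0.025, so 4 worsened users suffice. With P(X ≥ 4) in place of P(X ≥ 6), both nozzles miss 33% at w=10% (pooled 9%) and 6% at w=15% (pooled 0.7%). The direction holds, but the loss is smaller.

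**Paired t-test.** Power is from the noncentral t with n − 1 degrees of freedom, two-sided 5%, for standardised change d.

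| Assumed d | Power, n=33 | Both nozzles miss | Pooled miss (n=66) |
|---|---|---|---|
| 0.30 | 39% | 38% | 33% |
| 0.35 | 50% | 25% | 20% |
| 0.40 | 61% | 15–16% | 11% |
| 0.50 | 80% | 4% | 2% |

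If either nozzle's signal counts, the loss is about 2 to 5 points, with a family-wise error of 1 − 0.95² = 9.75%. If both nozzles must be significant, power at d=0.35 is only 25%.

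**Precision.** If no user worsens, the one-sided 95% upper limit is 1 − 0.05^(1/n): 8.7% for n=33 and 4.4% for n=66.

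**Against control.** The standard error factor is √(1/33 + 1/24) = 0.268 per nozzle and √(1/66 + 1/24) = 0.238 pooled, about 11% smaller. The difference detectable with 80% power falls from 0.77 to 0.68 SD.

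**The case against.** The strongest objection is that *product* may mean the spray. The Design row uses it in the singular, and the sample-size bullet speaks of the product fitted with one diffuser or the other. On that reading the within-group test already has 66 users. This cannot be excluded, but it leaves *each product* and the plural *products* with little to refer to. The ambiguity itself needs repair.

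Per-nozzle analysis also has a purpose. It matches the secondary aims, and pooling can dilute a harm confined to one nozzle. It should stay, and it would be wrong to say that precision is given up for nothing.

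A reader might infer two stronger points that the documents do not support:

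- **That the sizing contradicts the tests.** The bullet that gives 66 also gives 33 + 33, and no power basis shows that either number was the intended test size.
- **That every primary safety test is run per nozzle.** Clinical evaluation and adverse reactions are also primary endpoints, and no per-nozzle test is stated for them.

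Finally, only the synopsis and flow-chart are available, and the footers show a 64-page document. The absence of a pooled analysis is established for the synopsis alone.

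**Conclusion.** The point holds as an omission, not as a contradiction: the synopsis states no irritation analysis of all 66 spray users, although the primary objective concerns the spray as a whole. It rests on reading *product* as nozzle, which is the natural but not the only reading.

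The size depends on the test. Under the exact signed-rank fallback, which a 0 to 3 score would almost surely trigger, an assumed 15% one-grade worsening with no improvement is missed in both nozzles 39% of the time, against 6% pooled. With paired t-tests and either nozzle's signal accepted, the loss is small. The gain in precision does not depend on that choice: with no worsening seen, the upper limit is roughly halved. The change is worth making because it is cheap, and it does not call the design into question.

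**What to change.** 1. Define *product* in the Statistical methods row, and say whether the control group is part of the between-product comparison.
2. For the primary irritation endpoint, prespecify an all-spray estimate (66 evaluable) of the change from D0 to D90 and of the proportion worsened, each with a 95% interval (exact for the proportion). Add all-spray versus control.
3. Report adverse events for all spray users (72 included) as the proportion of subjects affected, with an exact interval.
4. Keep the per-nozzle results and the nozzle difference beside the pooled figures, so that a harm confined to one nozzle stays visible.
5. Leave obstruction as planned by nozzle, because the secondary aims are stated that way.

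The cost is some wording and one extra table column. No subjects, visits or measurements are added. The wording should be settled before the data are examined.

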Exclusion criteria:	
 
1. Subjects who had surgical act on the mastoïde.
 
2. Subjects who had severe troubles of the internal ear (severe dizziness, desorientation, nausea).
 
3. Subjects using regularly a ear spray for washing his/her ears.
 
4. Subjects having a score of ear canal obstruction at 4 at D0.
 
5. Pregnant or nursing woman or planning a pregnancy during the study;
 
6. Subject who had been deprived of their freedom by administrative or legal decision or who is under guardianship;
 
7. Subject in a social or sanitary establishment;
 
8. Subject suspected to be non-compliant according to the investigator's judgment;
 
9. Subject with a condition or receiving a medication which, in the investigator's judgment, put the subject at undue risk;
 
10. Subject suffering from a severe or progressive disease.
 

Investigational device: Name / code	
OCEAN BIO-ACTIF Ear Hygiene (reverse nozzle)
 
OCEAN BIO-ACTIF Ear Hygiene (microdiffusion nozzle)
 
Bag on valve spray, with ergonomic nozzle

YSLAB	Medical Device CIP #23E1670	Final version 2.0 Date: 09/11/2023	Confidential Page 12/64
-------	--------------------------------	---------------------------------------	----------------------------

Galenic form	2 sprays in ear, every 3 days at home
Dosage	90 days
Duration	Topical to ear canal
Administration route	
Endpoints:	
Primary endpoints:
 
 
• Clinical evaluation,
 
• Clinical score of the irritation with structured scale,
 
• Record of the possible adverse reactions.
 
 
Secondary endpoints:
 
 
• Clinical score of the obstruction of ear canal,
 
• Results of audiogram with classification of the loss or win hearing function
 
• Subject satisfaction survey
 
• The number of auricular affection (such as otitis) during the use period
 

Study Procedures:	D0, D90

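### The primary aim is to confirm safety, but the synopsis shows only two difference tests for the irritation score and no rule for concluding that the spray is safe

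*Combined protocol and SAP*

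**What the plan says.** All references are to the combined protocol and SAP, section 1.5 (overall synopsis), unless stated.

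- **Objectives:** "The primary objective of the study is to confirm the safety of a marketed auricular spray". The means listed are ENT examination, an irritation score from 0 to 3 compared with D0, and collection of adverse events.
- **Endpoints:** three primary endpoints: clinical evaluation, the irritation score, and "Record of the possible adverse reactions".
- **Statistical methods, primary endpoint:** two tests on the irritation score. The first, for each product, is that "a paired t-test will be used to test whether the change from baseline (D90-D0) differ significantly from 0", with a signed-rank test if Shapiro-Wilk rejects normality at 0.01. The second is introduced by "To test whether the products differ statistically in terms of change from baseline (D90-D0") and is a two-sided t-test with a Wilcoxon fallback. All tests are two-sided at 5%.
- **Statistical methods, opening lines:** safety/tolerance parameters are to be analysed on a safety population. No method is given there.
- **Design and sample size:** "tested product versus control group, in parallel groups"; "1 group of 72 included subjects in order to have results on 66 subjects", split 33 and 33 by nozzle; and "1 group of 27 included subjects in order to have results on 24 subjects not using a spray".

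**The concern.** A difference test asks whether the data contradict no change. A significant result can show harm. A non-significant result says only that harm was not detected, and in small groups that is a weak statement. The synopsis attaches no limit or bound to the irritation score, the clinical evaluation or the adverse reactions, so it does not show what result would count as safety confirmed.

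What is at stake is the primary conclusion. Two non-significant p-values could be reported as confirmation of safety while about 1 user in 11 of a nozzle has new irritation and the data remain compatible with about 1 in 4.

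**Working it through.** **Inputs from the synopsis.** Evaluable subjects: 33 per nozzle and 24 controls. Two-sided 5% level. Change defined as D90 minus D0. The sums agree (33 + 33 + 24 = 90 evaluable; 72 + 27 = 99 included). The supplied text gives no effect size, event rate, margin or power, so there is no sample-size calculation to reproduce.

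**Assumptions (mine, for illustration).** k subjects worsen by one grade, the rest do not change, none improve, one score per subject, no worsening in control.

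**Test 1, change against zero, n = 33.** With k equal positive changes the exact signed-rank p is 2 × 0.5^k. The text does not say exact or approximate, so the variants are shown.

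| k/33 | exact signed-rank | normal, corrected | normal, uncorrected | paired t |
|---|---|---|---|---|
| 3 | 0.25 | 0.149 | 0.083 | 0.083 |
| 4 | 0.125 | 0.072 | 0.046 | 0.044 |
| 5 | 0.0625 | 0.037 | 0.025 | 0.023 |
| 6 | 0.031 | 0.020 | 0.014 | 0.012 |

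Shapiro-Wilk gives p < 1e-9 for 3 to 5 ones among 33, so the signed-rank fallback is the likely route.

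**Test 2, between groups.** I used the rank-sum test for the non-parametric case because the arms are parallel; the fallback named in the text is a signed-rank test, which is for paired data.

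- 3/33 against 0/24: rank-sum 0.133, pooled t 0.134, Welch 0.083, Fisher 0.256.
- 5/33 against 0/24: rank-sum 0.048, pooled t 0.047, Fisher 0.067.
- 3/33 in both nozzles, nozzle against nozzle: p = 1.

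**What 3/33 leaves open.** 3/33 = 9.1%, exact (Clopper-Pearson) 95% CI 1.9% to 24.3%. Difference from 0/24: 95% CI −5.9 to +23.6 points (Newcombe).

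**If the nozzles are pooled, n = 66.** Three in each nozzle becomes 6/66. Against zero change this is significant: exact signed-rank 0.031, paired t 0.013. Against 0/24 it is not by rank-sum (0.128) or pooled t (0.129), but is by Welch (0.013). With 3/66 (4.5%, 95% CI 0.9% to 12.7%), test 1 is non-significant in every variant (0.083 to 0.25).

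**How often nothing is flagged if the true worsening rate is 10%, with none in control.**

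- *One nozzle, against zero and against control.* With t-tests nothing is flagged when X ≤ 3: P(X ≤ 3 | 33, 0.10) = 0.577. With exact signed-rank plus rank-sum nothing is flagged when X ≤ 4, because the rank-sum flags 5/33: P(X ≤ 4) = 0.770.
- *Both nozzles at 10%, all per-nozzle tests counted.* With t-tests: 0.577² = 0.333. With exact signed-rank plus rank-sum: 0.7697² = 0.592, less the pairs (0, 4) and (4, 0), which the nozzle-against-nozzle rank-sum flags (p = 0.041): 2 × 0.0309 × 0.1927 = 0.012. This leaves 0.580.
- *Pooled, against zero only.* P(X ≤ 3 | 66, 0.10) = 0.093 (t-test) and P(X ≤ 5) = 0.343 (exact signed-rank).

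**Best case under estimation.** With zero events the exact two-sided 95% upper limit is 1 − 0.025^(1/n): 10.6% for n = 33 and 5.4% for n = 66. The one-sided 95% version, 1 − 0.05^(1/n), gives 8.7% and 4.4%.

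**The case against.** - **The plan never equates non-significance with safety.** True. A reader might infer that it does, but no sentence says so. What stands is that the synopsis shows no other rule linking the primary result to the aim.
- **Safety has other routes.** Also true in part. ENT examination and adverse events belong to the primary endpoints, and a separate safety/tolerance analysis is announced. It would be too strong to say that the plan has no other route; but no criterion or method is shown for any of these.
- **Only part of the plan is visible.** The supplied pages carry footers 11 to 13 of 64, and the population sentences have gaps. A reader might infer that the whole plan lacks a success rule or a sample-size rationale. The supplied text cannot support that. Even so, a synopsis that states the aim and the primary tests should state the rule that joins them.
- **The example depends on analysing by nozzle.** It does. The 33/33 split and the separate listing of nozzles under the secondary aims support that reading without settling it. Pooled, the same events are significant against zero change, so it is wrong to say that 3 per nozzle would pass both tests on any reading.
- **A post-market study may use the word confirm descriptively.** Possible. In that case the remedy is mostly wording, and cheap.

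**Conclusion.** The concern holds for the text supplied: the stated aim is confirmation, the tests shown for the primary score can only detect a difference, and no limit, bound or success rule is shown. This is a mismatch between aim and analysis and should be fixed.

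Its size depends on the unit of analysis. Per nozzle, 3/33 is non-significant on both tests while a rate of up to 24% is not excluded. A true 10% rate goes unflagged 58% to 77% of the time if one nozzle is considered, and about 33% to 58% if both nozzles worsen and every per-nozzle test counts. Pooling is more sensitive: 6/66 is flagged against zero change and 3/66 is not. The tests are therefore not blind to harm, and the 58% to 77% range should not be quoted as the miss rate for the whole study.

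These figures rest on one-grade changes, no improvers, no worsening in control and the planned evaluable numbers.

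Separately, and adding no weight here, the Objectives specify "scoring of the irritation of the ear canal at D60 in comparison with basal scoring of irritation at D0", whereas the study procedures, the statistical methods and the flow-chart use D90. These places must be reconciled.

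**What to change.** 1. As the primary safety result, report for each nozzle (and pooled, if intended) the proportion whose irritation score at the assessment visit (D90 in the analysis text) is at least one grade above D0. Give an exact two-sided 95% CI, matching the plan's two-sided 5% level, and the difference from control with a 95% CI.
2. Tabulate worsening by one, two and three grades, so that slight and severe changes are not merged.
3. Keep the two difference tests as descriptive, and state that non-significance is not read as confirmation of safety.
4. State whether a product means a nozzle or the pooled spray group, and whether control is part of the between-product comparison.
5. Reword the objective as estimation. If a confirmatory claim is wanted, the sponsor should fix a limit before seeing data, state the confidence level used, and check that the sample can meet it.
6. State the method of the safety/tolerance analysis, or point to where it is given.

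**Cost.** The estimation route is wording plus one table from scores already collected, with no extra subjects or visits. The downside is a less flattering conclusion: even with no events, the study could say only that the rate is below 10.6% per nozzle or 5.4% pooled (two-sided 95%). A confirmatory limit below those values could not be met at that level with the planned numbers.

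### A Shapiro-Wilk pre-test chooses the primary irritation test; when few subjects change it always picks the signed-rank test, and when nobody changes no test is defined

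*Combined protocol and SAP*

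**What the plan says.** All references are to the combined protocol and SAP, section 1.5 (synopsis). Safety is the principal aim. Under Statistical methods, Primary endpoint: "The irritation is assessed by the Laryngologist using a 4-point structured scale", at D0 and D90. (The objectives row names D60. The analysis text and the flow chart use D90, and so does this note.)

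The within-arm test is a paired t-test: "For each product, a paired t-test will be used to test whether the change from baseline (D90-D0) differ significantly from 0". Then "The normality assumption will be checked using a Shapiro-Wilk test" at level 0.01, and a rejection replaces the t-test by a Wilcoxon signed-rank test. The same rule is repeated for each secondary parameter, including the 0-4 obstruction score. Endpoint tests use 5%, "level of significance in a bilateral approach".

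On size, the plan has "1 group of 72 included subjects in order to have results on 66 subjects", split 33 and 33 by nozzle, and 27 control subjects included to give 24. The supplied pages do not say what is reported if no score changes, whether the signed-rank p-value is exact or approximate, or whether all arms must use the same test.

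**The concern.** The variable tested is a difference of two small integers. In a study meant to confirm the safety of a marketed spray, most irritation changes should be zero. Such data can never look normal, so the pre-test does not really choose: it sends the analysis to the signed-rank test whenever anyone changes. That test drops the zeros and works only from the few subjects who moved.

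Two things are at stake. A noticeable share of subjects could worsen and still be reported as showing no significant change, which a reader may take as reassurance. And if no subject changes at all, the stated rule returns no result.

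**Working it through.** **Inputs.** From the synopsis: 33, 33 and 24 evaluable subjects; irritation 0-3; Shapiro-Wilk level 0.01; endpoint tests two-sided at 5%. The plan gives no expected rate of change and no SD, so every rate and SD below is an assumption, shown as a range. The sample sizes add up (72+27=99; 66+24=90), but there is no power figure to reproduce.

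**Step 1: few subjects change.** Let k of n=33 worsen by one grade and the rest stay the same.

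- Paired t-test: the variance of the change is k(n-k)/[n(n-1)], so t = sqrt[k(n-1)/(n-k)] on 32 df. For k=5, t = sqrt(5×32/28) = 2.39.
- Exact signed-rank, all changes in one direction: p = 2×0.5^k. For k=5, p = 0.0625.
- Signed-rank with an uncorrected normal approximation: z = sqrt(k). For k=5, z = 2.24.

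| k of 33 | Shapiro-Wilk p | t-test p | exact signed-rank p | normal-approximation p |
|---|---|---|---|---|
| 3 (9%) | 3.6e-11 | 0.083 | 0.25 | 0.083 |
| 4 (12%) | 1.2e-10 | 0.044 | 0.125 | 0.046 |
| 5 (15%) | 3.4e-10 | 0.023 | 0.0625 | 0.025 |
| 6 (18%) | 8.7e-10 | 0.012 | 0.031 | 0.014 |

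For k=1 to 7 the Shapiro-Wilk p-value is at most 2e-9 (n=24: at most 3.2e-7), so the signed-rank test is always selected. With an exact p-value at least 6 changes are needed at any n. In an arm of 24, 5 changes (21%) also fall short.

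**Step 2: what that costs.** If the true chance of a one-grade worsening is 10%, the chance of 6 or more among 33 is 11%; the t-test needs only 4 or more, which has probability 42%. At 15% the figures are 37% and 75%.

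**Step 3: nobody changes.** The SD is 0, so the t-test is 0/0, there is no spread on which to assess normality, and the signed-rank test has no non-zero difference. The probability is (1-q)^n for a chance of change q:

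- q=5%: 0.95^33 = 18%; 0.95^24 = 29%; at least one of three arms, 1-(1-0.184)²(1-0.292) = 53%.
- q=2%: 0.98^33 = 51%.

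**Step 4: obstruction.** Entry requires "Subjects having a clinical score of ear canal obstruction of 2 or 3 at D0", so the change runs from -3 to +2. I simulated D0 scores of 2 or 3 with equal chance and D90 as a rounded normal value limited to 0-4, with mean 1.2 to 2.5.

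- An arm of 33 and an arm of 24 receive different tests in about 47-56% of trials at a D90 SD of 0.9-1.0, 22-31% at SD 0.7, and 2-4% at SD 0.5.
- With the normal approximation, the t-test and signed-rank test disagree at 5% in about 1% of arms or fewer in most settings, and in under 3% in all.
- With exact p-values they disagree in up to about 5%, except for 9-12% in one setting (mean 2.2, SD 0.5). There at least 97% of arms receive the signed-rank test anyway.
- Across the no-change scenarios tried for irritation and obstruction, the two-stage rule had type I error between 0.0007 and 0.044.

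**The case against.** The strongest reply is that the pre-test causes little of this. With no changes the t-test is undefined too, so deleting the pre-test alone cures nothing. With few one-directional changes, the switch alters the conclusion only at k=4 or 5, and only if the p-value is exact; under the uncorrected approximation both tests first reach 5% at k=4. An all-zero arm would in practice be reported as 0 of 33. Worsening is not hidden either, because clinical evaluation and adverse reactions are also primary endpoints. All of this stands. It narrows the point but leaves a primary rule with an undefined outcome, and on these pages an unstated p-value method that decides the result at k=4 or 5.

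A reader might infer that arms will often receive different tests and so cannot be compared. The documents do not support that. The frequency runs from 2% to 56% with an assumed SD that the plan does not give, the two tests seldom disagree, and the arms have their own between-product comparison. When irritation changes are few, every arm with any change receives the same test. Nor is there inflated type I error: the rule is conservative.

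Finally, the supplied pages are a synopsis and a flow chart from a 64-page plan. Silence here on zero variance or exact p-values does not show that the full plan is silent.

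**Conclusion.** The point holds for the primary irritation score. When few subjects change, the pre-test always leads to the signed-rank test. With an exact p-value, up to 5 changed subjects (15% of 33, 21% of 24) cannot reach significance; with an uncorrected normal approximation the limit falls to 3. When nobody changes, neither test exists, which has probability 18% to 51% in an arm of 33 if each subject has a 5% to 2% chance of change. Those rates are assumptions. A non-significant result under this rule is weak support for the aim of confirming safety.

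The wording may exclude the control arm from the within-arm test, or pool the two nozzles. The exact minimum of 6 changes is the same in either case.

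For obstruction, the data-driven choice is untidy but rarely affects a conclusion.

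**What to change.** Delete the Shapiro-Wilk step for irritation. Pre-specify, for every arm, the number and percent with an increase of at least one grade from D0 to D90, with an exact (Clopper-Pearson) 95% confidence interval. This is defined for every outcome and states what the data can rule out: 0/33 gives an upper limit of 1-0.025^(1/33) = 10.6%; 0/24 gives 14.2%; 5/33 gives 5.1% to 31.9%. Mean change and t-test output can stay as descriptive.

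For obstruction, name one test for all arms as a minor tidy-up.

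The cost is wording only, with no new data and no extra subjects. The downside is that the primary irritation result becomes an estimate with an interval rather than a p-value.
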